5.1 INCLUSION CRITERIA

The inclusion criteria listed in the master protocol are only those applicable to all the participants common to all substudies. For additional substudy specific criteria, refer to the particular substudy.

Participants are eligible to be included in the study only if all of the following criteria apply for a given cohort:

Age

I 01. Participant must be ≥ 12 years of age, at the time of signing the informed consent.

See requirement specific to France in Appendix 7 ([Section 10.7](#)).

Type of participant and disease characteristics

I 02. Provision of tumor tissue:

- Disease location amenable to mandatory tumor biopsy (optional for participants ≥ 12 and <18 years of age) at baseline unless clinically unfeasible (minimum 10 slides with 4-5 micron thickness for the participants who have signed ICF [excluding screen failure participants]) and possibly at Cycle 2 Day 1. Fine needle aspirates are not acceptable. Availability of a tissue specimen from core needle or excisional biopsies, or resected tissue are required. Provision of archival tumor tissue sample obtained within 6 months (there should be no systemic anti-cancer therapy between collection of biopsy and enrollment) is allowed to replace mandatory baseline biopsy.

Note: Clinically unfeasible biopsy should be documented by a written communication from the Investigator to the Sponsor that performing a biopsy will put the wellbeing of the subject at an excessive risk.

- The Sponsor may approve the written request to enroll, on a case-by-case basis, participants with:
 - Location of the tumor not amenable to biopsy due to significant risk, OR
 - Less than required number of slides or archival tumor tissue sample collected more than 6 months prior to screening.

I 03. Measurable disease:

The participant must have relapsed or refractory disease. Measurable disease defined as at least one measurable node that must have an LDi (longest diameter) >1.5 cm and/or measurable extranodal lesion that must have a LDi >1 cm according to Lugano response criteria 2014. Tumor sites that are considered measurable must not have received prior radiotherapy, unless among them at least one is FDG-avid.

Weight (not applicable)**Sex, contraceptive/barrier method and pregnancy testing requirements**

I 04. All (male and female)

Contraceptive use by men and women should be consistent with local regulations regarding the methods of contraception for those participating in clinical studies.

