skin, or carcinoma in situ (eg, breast carcinoma, cervical cancer in situ) that have undergone potentially curative therapy are not excluded.

- E 19. Known severe hypersensitivity (\geq Grade 3) to or contraindication for the use of any study intervention or components thereof, including premedication to be administered in this study, as well as PEG or any pegylated drug and *E. coli*-derived protein.
- E 20. Participants with baseline oxygen saturation (SpO_2) \leq 92% (without oxygen therapy).

Prior/concomitant therapy

- E 21. Has received prior IL2-based anticancer treatment.
- E 22. Is unable or unwilling to take premedication.
- E 23. Deleted by protocol amendment 01.
- E 24. Deleted by protocol amendment 01.

Prior/concurrent clinical study experience

- E 25. Current enrollment or past participation in a study of an investigational treatment or has used an investigational device within 28 days prior to the first dose of study treatment.

Note: Participants who have entered the follow-up phase of an investigational study may participate as long as it has been 28 days after the last dose of the previous investigational treatment.

Organ and bone marrow function

- E 26. Absolute neutrophil count $<1000/\mu\text{L}$ ($1 \times 10^9/\text{L}$) (after at least one week off G-CSF).
- E 27. Platelets $<50 \times 10^3/\mu\text{L}$ (after at least 3 days without platelet transfusion).
- E 28. Hemoglobin $<9 \text{ g/dL}$ or $<5.6 \text{ mmol/L}$ (after at least 1 week without packed red blood cell [pRBC] transfusion. Participants can be on stable dose of erythropoietin (\geq approximately 3 months)).
- E 29. Total bilirubin $>1.5 \times$ upper limit of normal (ULN) unless direct bilirubin \leq ULN (participants with known Gilbert disease who have serum bilirubin level $\leq 3 \times$ ULN may be enrolled).
- E 30. Aspartate aminotransferase (AST) and/or alanine aminotransferase (ALT) $>2.5 \times$ ULN (or $>5 \times$ ULN for participants with lymphoma involving the liver).
- E 31. Estimated glomerular filtration rate (eGFR) $<50 \text{ mL/min}/1.73 \text{ m}^2$ (Modification of Diet in Renal Disease [MDRD] Formula, see [Section 10.2 Appendix 2](#)).

E 32. International Normalized Ratio (INR) or Prothrombin Time (PT) (or Activated Partial Thromboplastin Time [aPTT]) $>1.5 \times \text{ULN}$ unless the participant is receiving anticoagulant therapy as long as PT or aPTT is within therapeutic range of intended use of anticoagulants.

Other exclusions

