10.2 APPENDIX 2: CLINICAL LABORATORY TESTS

- The tests detailed in [Table 6](#) will be performed by the local laboratory.
- Protocol-specific requirements for inclusion or exclusion of participants are detailed in [Section 5](#).
- Additional tests may be performed at any time during the study as determined necessary by the Investigator or required by local regulations.

Table 6 - Protocol-required laboratory assessments

Laboratory tests	Parameters
Hematology ^a	Platelet count Hemoglobin Hematocrit White blood cell (WBC) count with differential: Neutrophils Lymphocytes Monocytes Eosinophils Basophils
Clinical chemistry ^a	Urea or blood urea nitrogen (BUN) Creatinine and eGFR (MDRD formula ^b) Glucose Potassium Sodium Corrected Calcium Phosphate Chloride Magnesium Bicarbonate ^c Aspartate aminotransferase (AST)/ Serum glutamic-oxaloacetic transaminase (SGOT) Alanine aminotransferase (ALT)/ Serum glutamic-pyruvic transaminase (SGPT) Alkaline phosphatase Total and direct bilirubin Total protein Lactate dehydrogenase (LDH) Albumin Amylase Lipase
Endocrine function tests ^d	Thyroid-stimulating hormone (TSH) Tri-iodothyronine (T3) Free thyroxine (FT4) Cortisol (preferably in the morning)
Coagulation	International normalized ratio (INR) or Prothrombin Time (PT) (or Activated Partial Thromboplastin Time [aPTT])
Routine urinalysis	
 Specific gravity, pH, glucose, protein, blood, ketones, and leukocytes by dipstick Microscopic examination (if blood or protein is abnormal)
Other screening tests	
 Follicle-stimulating hormone and estradiol may be used to confirm a postmenopausal state in women not using hormonal contraception or hormonal replacement therapy (HRT) Highly sensitive serum or urine human chorionic gonadotropin (hCG) pregnancy test (as needed for women of childbearing potential) ^e Serology (hepatitis B surface antigen [HBsAg], hepatitis C virus antibody), Hepatitis

B viral load, HCV RNA level, CD4 counts & HIV viral Load^f

- Troponin
- The results of each test must be entered into the e-CRF

NOTES:

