- a Blood Chemistry/hematology should be done with an overnight fasting if possible (should not interfere with hydration requirements). It will be performed weekly on D1 pre-dose, D8 and D15 (D15 for participants who receive Q3W only) during Cycle 1, then on Day 1 of every cycle up to Cycle 12, then every other cycle during Treatment Phase. Visits and assessments on C1D2-D3 will be performed for participants in the safety run-in or participants who are hospitalized because of high tumor burden or at Investigator's discretion. During the Observation Period, it will be performed at Follow-Up Visit 1. It can also be performed as clinically indicated. In case of Grade ≥ 3 liver function abnormal tests, additional tests will be repeated every 2-3 days until recovery to baseline value.
- b Modification of Diet in Renal Disease (MDRD) equation: Glomerular filtration rate (mL/min/1.73 m²) = 175 × (Serum Creatinine)-1.154 × (Age)-0.203 × (0.742 if Female) × (1.212 if African American)
- c Bicarbonate or carbon dioxide (venous) (if bicarbonate or carbon dioxide are assessed only on arterial blood at site level, to be done only if clinically indicated)
- d Endocrine function tests will be performed every 2 cycles throughout the entire treatment period and at EOT. During the Observation Period, they will be performed at Follow-Up Visit 1. They can also be performed as clinically indicated.
- e Pregnancy Test: Women of childbearing potential must have a negative urine pregnancy test result within 72 hours prior to first IMP administration of each cycle, at EOT and every 30 (± 7) days until 120 days (or refer to the individual substudy protocol) after the last dose of study treatment. If urine pregnancy results cannot be confirmed as negative, a serum pregnancy test will be required. Pregnancy tests (serum and/or urine tests) should be repeated if required by local guidelines.

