Clinical tumour lysis syndrome (CTLS) assumes the laboratory evidence of metabolic changes and significant clinical toxicity that requires clinical intervention. CTLS is defined as the presence of LTLS and any one or more of the above-mentioned criteria.

*Not directly or probably attributable to a therapeutic agent (e.g. rise in creatinine after amphotericin administration).

† Creatinine levels: patients will be considered to have elevated creatinine if their serum creatinine is 1.5 times greater than the institutional upper limit of normal (ULN) below age/gender defined ULN. If not specified by an institution, age/sex ULN creatinine may be defined as: $> 1 < 12$ years, both male and female, $61.6 \text{ } \mu\text{mol/l}$; $\geq 12 < 16$ years, both male and female, $88 \text{ } \mu\text{mol/l}$; ≥ 16 years, female, $105.6 \text{ } \mu\text{mol/l}$; ≥ 16 years, male, $114.4 \text{ } \mu\text{mol/l}$.

For participants in the safety run-in or participants who are hospitalized because of high tumor burden or at Investigator's discretion, tumor lysis laboratory tests (corrected calcium, magnesium, phosphate, uric acid, and lactate dehydrogenase [LDH] levels) will be obtained per details provided in the individual substudy).

Cardiac monitoring and admission to the ICU is required if TLS is established, as well as continuing laboratory monitoring every 4-6 hours. Additional measures to treat metabolic derangements associated with TLS may be required, as shown in [Table 14](#).

Prophylaxis against TLS may be required depending on the patient's risk for TLS, as described below.

Low-risk is defined as:

- Patients with low tumor burden (WBC $\leq 50 \times 10^9/l$ and normal LDH level)
- Patients receiving low intensity cytoreductive therapy
- Normal pre-existing uric acid
- Adequate hydration
- No tumor infiltration in the kidney

High-risk is defined as:

- Hematological malignancies with high proliferative rate
- High tumor burden (WBC $\geq 50 \times 10^9/l$ and high LDH level)
- Elevated uric acid level
- Patients receiving intensive cytoreductive therapy
- Poor hydration
- Leukemia infiltration of the kidney

Recommendations for **intravenous hydration** during SAR444245 treatment in patients at high risk for TLS, include the following:

- [REDACTED]
- [REDACTED]
- [REDACTED]
- [REDACTED]

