- g Weight/Height: Height is required at baseline only for patients > or =18 years old. For trial participants <18 years old, height should be assessed on day 1 \pm 1 of each cycle. Weight is required at Screening and prior to starting each infusion. The total dose will be calculated based on the weight on the day of the infusion or the most recent weight assuming it was assessed in a reasonable time frame according to Investigator assessment. Study sites should make every effort to measure body weight as close to the infusion day as possible considering the variability of local process from site to site. If the infusion is prepared with the most recent weight assessed in a reasonable time frame, this will not prevent to assess the weight on D1 of each cycle.
- h Blood chemistry/ hematology will be performed weekly on D1 pre-dose, D8 and D15 during Cycle 1, then on Day 1 of every cycle up to Cycle 12, then every other cycle during Treatment Phase. Visits and assessments on C1D2-D3 are only for participants in the safety run-in or participants who are hospitalized because of high tumor burden or at investigator's discretion. For these participants, vital signs, SpO₂ and complete blood counts (CBC) and differentials, chemistries (blood urea nitrogen (BUN), creatinine (Cr), alanine transaminase (ALT), aspartate transaminase (AST), alkaline phosphatase (Alk Phos), total bilirubin (TBil) will be obtained daily.
- i Tumor lysis laboratory tests (corrected calcium, magnesium, phosphate, uric acid, and lactate dehydrogenase [LDH] levels) will be obtained every 8 hours on C1D1 for safety run-in participants or participants who are hospitalized, and C1D2-D3 for safety run in or participants who are hospitalized because of high tumor burden or at investigator's discretion.
- j Endocrine function tests will be performed every 2 cycles throughout the entire treatment period and at EOT. During the Observation Period, they will be performed at Follow-Up Visit 1. They can also be performed as clinically indicated.
- k Coagulation includes international normalized ratio (INR), prothrombin time (PT) and activated partial thromboplastin time (aPTT).
- l Urinalysis will be performed on C1D1 and C2D1, then as clinically indicated during the treatment period, and will be performed at Follow-Up Visit 1.

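### Renal exclusion E 31 applies one MDRD equation from age 12, so its cut-off tolerates far higher creatinine, relative to the protocol's own age-specific limits, in 12- to 15-year-olds than in adults

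*Protocol*

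**What the plan says.** - **Age range.** Master protocol 5.1, I 01: "Participant must be ≥ 12 years of age". Appendix 7 raises this to 18 in France only.
- **Renal entry rule.** Master protocol 5.2, E 31, excludes on "Estimated glomerular filtration rate (eGFR") below 50 mL/min/1.73 m², names the "Modification of Diet in Renal Disease [MDRD] Formula", and points to Appendix 2. It has no age restriction.
- **Equation.** Appendix 2, Table 6 lists "Creatinine and eGFR (MDRD formula") as the only eGFR method. Footnote b gives it as "175 × (Serum Creatinine)-1.154 × (Age)-0.203 × (0.742 if Female) × (1.212 if African American"), with no unit for creatinine and no height or body-size term.
- **Age-specific creatinine limits.** Appendix 12, in the tumor lysis syndrome (TLS) definitions, gives fallback values where the site has none ("age/sex ULN creatinine may be defined as"): 88 µmol/L for ages 12 to under 16 in both sexes, and from age 16, 105.6 µmol/L for females and 114.4 µmol/L for males. It treats 1.5 × ULN as elevated.
- **Role of the rule.** Appendix 10, Table 8 names entry eGFR first among the nephrotoxicity mitigations, followed by regular renal monitoring and dose-modification guidance.
- **SAP.** Section 3.6.3.1 analyses eGFR against potentially clinically significant abnormality (PCSA) criteria. Section 3.7.2 and Appendix 3 use an age category of 12 to under 18.

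Neither substudy adds an equation for participants under 18 or a creatinine limit at entry.

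**The concern.** Two things move in opposite directions below age 16. The age term in the equation raises the eGFR for a given creatinine as age falls, so more creatinine is allowed before the estimate drops below 50. Over the same ages, the protocol's own default ULN is lower than the adult value. A single eGFR floor then corresponds to very different degrees of creatinine elevation in a young adolescent and an adult.

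What is at stake is the screening function of E 31. It is the only numeric renal limit at entry, and Table 8 also records a related acute kidney injury in the first-in-human study. A participant who passes E 31 gives the site no numeric prompt to look further. Elsewhere the protocol does adapt to age: Lansky scale below 16, pediatric ICANS grading, and age-banded creatinine and phosphorus limits in Appendix 12.

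**Working it through.** The plan states no creatinine equivalent of E 31, so there is no figure of its own to reproduce. The check solves the printed equation for the creatinine at which eGFR equals 50.

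**Inputs**
- Equation: Appendix 2, Table 6 footnote b, with the flat-printed -1.154 and -0.203 read as exponents.
- Cut-off 50: E 31.
- ULNs 88, 105.6 and 114.4 µmol/L, and the 1.5 × level: Appendix 12.
- Creatinine unit: assumed mg/dL, at 88.4 µmol/L per mg/dL. Entering µmol/L directly gives an eGFR of 0.60 for a boy of 12 at 88 and 0.35 for a man of 40 at 114.4, so mg/dL is the only workable reading.
- The 1.212 factor is not applied unless stated.

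**Formula**

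Scr = (175 × age^-0.203 × sex factor / 50)^(1/1.154), with sex factor 1 for males and 0.742 for females.

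Boy of 12: 175 × 12^-0.203 = 175 × 0.604 = 105.7. Then 105.7 / 50 = 2.113, and 2.113^(1/1.154) = 1.913 mg/dL = 169.1 µmol/L. Finally 169.1 / 88 = 1.92 × ULN.

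Man of 40: 175 × 40^-0.203 = 175 × 0.473 = 82.8. Then 82.8 / 50 = 1.655, and 1.655^(1/1.154) = 1.548 mg/dL = 136.8 µmol/L. Finally 136.8 / 114.4 = 1.20 × ULN.

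| Participant | Creatinine at eGFR 50 (µmol/L) | Default ULN (µmol/L) | Multiple of ULN | eGFR at 1.5 × ULN |
|---|---|---|---|---|
| Boy, 12 | 169.1 | 88 | 1.92 | 66.5 (passes) |
| Boy, 15 | 162.6 | 88 | 1.85 | 63.6 (passes) |
| Girl, 12 | 130.5 | 88 | 1.48 | 49.4 (excluded) |
| Girl, 15 | 125.5 | 88 | 1.43 | 47.2 (excluded) |
| Boy, 16 | 160.7 | 114.4 | 1.40 | 46.4 (excluded) |
| Boy, 17 | 159.0 | 114.4 | 1.39 | 45.8 (excluded) |
| Man, 40 | 136.8 | 114.4 | 1.20 | 38.5 (excluded) |
| Woman, 40 | 105.6 | 105.6 | 1.00 | 31.3 (excluded) |

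**Source of the gap.** The allowed creatinine for a boy of 12 is 169.1 / 136.8 = 1.24 times that for a man of 40, so 24% higher. His default ULN is 88 / 114.4 = 0.77 of the man's, so 23% lower. Together, 1.24 × (114.4 / 88) = 1.24 × 1.30 = 1.61, which matches 1.92 / 1.20 = 1.60 up to rounding.

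**Sensitivity**
- Conversion at 88.0 instead of 88.4: boys of 12 to 15 at 1.91 to 1.84 ×, man of 40 at 1.19 ×.
- With the 1.212 factor: boys of 12 to 15 at 2.27 to 2.18 ×, man of 40 at 1.41 ×.
- Local ULN for a boy of 12 anywhere from 80 to 105 µmol/L (assumed range): 169.1 / 80 = 2.11 × to 169.1 / 105 = 1.61 ×. To bring him to the man's 1.20 ×, his ULN would have to be 169.1 / 1.20 = 141 µmol/L, above the adult male default.

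**The case against.** **A multiple of ULN is not a measure of kidney function.** Any age- and sex-adjusted eGFR cut-off gives unequal multiples, including among adults: 1.00 × for a woman of 40 and 0.91 × for a woman of 70. This stands as a limit on what the figures prove. A reader might infer that E 31 admits adolescents with impaired kidneys. The documents do not support that: they give no second GFR estimate at these ages and do not discuss MDRD's validity under 18. The inconsistency remains, because among adults the default ULN is constant within sex, whereas below 16 the allowed creatinine rises while the protocol's own limit falls.

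**The ULNs are fallback values from the TLS appendix, and safety laboratories are local.** True, so the multiples shift by site. The step at age 16 shows how much rests on the banding: at the same 160.7 µmol/L the multiple drops from 1.83 to 1.40. The 24% higher absolute tolerance does not depend on any ULN.

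**The 1.5 × ULN comparison is narrow.** It is. Only boys of 12 to 15 pass at that level, so it should not be read as covering all adolescents. Nor would such a boy meet the definition of clinical TLS: creatinine is one component, and laboratory TLS is also required.

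**There are other safeguards.** E 11 excludes ongoing Grade 2 or higher toxicity from prior anticancer therapy (with listed exceptions), E 35 and E 38 allow exclusion on the investigator's judgement, and Table 8 adds monitoring and dose-modification guidance. E 31 is therefore not the sole protection, but none of these sets a numeric renal limit at entry.

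**The SAP names no eGFR equation.** A reader might infer that its eGFR tables for participants under 18 are distorted. That cannot be shown: the PCSA thresholds sit in an external sponsor list, and creatinine is analysed separately. What stands is that the SAP leaves the method unstated.

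**Conclusion.** The point holds as an inconsistency between E 31 with Appendix 2 and the age-specific creatinine limits in Appendix 12. Outside France, the stated rule starts to exclude boys of 12 to 15 at 1.85 to 1.92 × the default ULN and girls of that age at 1.43 to 1.48 ×, while 40-year-olds are excluded from 1.20 × (men) and 1.00 × (women). Boys of 12 to 15 from 1.5 × up to those cut-offs are left to investigator judgement and on-study monitoring.

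This rests on creatinine in mg/dL, the Appendix 12 defaults, and omission of the 1.212 factor. The direction survived each variation tried. The documents do not say how many participants would fall in the affected range; with about 25 per cohort it is likely to be few. The change is worth making because it is a safety gate and the correction is cheap.

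**What to change.** 1. In E 31 and Table 6 footnote b ("Modification of Diet in Renal Disease (MDRD) equation: Glomerular filtration rate"), specify an eGFR method suited to participants under 18 and reconcile it with the creatinine limits in Appendix 12. The choice of equation, and whether the cut-off of 50 carries over to it, is for the sponsor to make and justify. MDRD can remain for adults.
2. State the creatinine unit in footnote b.
3. In SAP 3.6.3.1, name the eGFR method and use the same one for participants under 18.

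The cost is a short text change in each place. A height-based estimate would need no new measurement: the schedule of activities marks height at screening, and for participants under 18 footnote g repeats it every cycle ("years old, height should be assessed on day 1"). The downside is that a few adolescents near the cut-off may become ineligible.

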5.3 LIFESTYLE CONSIDERATIONS

5.3.1 Meals and dietary restrictions

No food or drink restrictions are required. Guidelines on fluid intake are presented in [Section 6.1.3](#).

5.3.2 Caffeine, alcohol, and tobacco

No restrictions are required.

5.3.3 Activity

Participants are advised to abstain from strenuous exercise and avoid long hot showers and saunas on Days 1 to 4 of every treatment cycle.

5.3.4 Hydration

Since SAR444245 may induce episodes of hypotension, participants should be informed of the importance of being well hydrated and provided hydration instructions. Guidelines pertaining to fluid intake on the day of SAR444245 dosing and for the 3 days after administration are detailed in [Section 6.1.3](#).

5.4 SCREEN FAILURES

Screen failures are defined as participants who consent to participate in the clinical study but are not subsequently enrolled. A minimal set of screen failure information is required to ensure transparent reporting of screen failure participants to meet the Consolidated Standards of Reporting Trials (CONSORT) publishing requirements and to respond to queries from regulatory authorities. Minimal information includes demography, screen failure reasons, eligibility criteria, and any serious adverse event (SAE).

Individuals who do not meet the criteria for participation in this study (screen failure) and for whom resolution of the screen failure reason may not be expected within a reasonable time frame, will be recorded as screen failures. In case the participant is a temporary screen failure (ie prolonged screening), there is no need to have participant (or the participant's legally authorized representative) re-consent (ie, new ICF signed) if the participant finally participates in the trial. However, if the reason for temporary screen failure is a reason that might have altered the initial given agreement of the participant to participate, the Investigator should ensure the willingness of the participant to continue or redo some screening procedures and his/her participation to the trial. This oral agreement should be documented in the participant's chart. All the tests out of protocol window should be repeated and entered to the additional pages.

A participant who screen failed may be rescreened; in this situation, the rescreened participant (or the participant's legally authorized representative) should sign a new ICF. A participant may be rescreened only once. Rescreened participants should be assigned a different participant number as for the initial screening.

